## Approach

Our central hypothesis is that brain anatomy impacts the efficacy of iTBS therapy. The basis for this hypothesis is that anatomical complexities of cortical motor regions and their corresponding fiber tracts determine TMS induced electric fields in the brain, and these electric fields are the mechanistic drivers of TMS-based therapies. The rationale for our proposed research is that elucidating the impact of brain anatomy on the efficacy of iTBS is beneficial for two primary reasons: 1) imaging techniques provide the opportunity to identify the best patients for iTBS therapy based on their brain anatomy, and 2) stimulation therapy could be optimized based on the patient's brain anatomy. Thus, the effect of brain anatomy on iTBS efficacy is important to tailor rehabilitation appropriately.

In order to determine the effect of brain anatomy on the induced electric fields acting on cortical neural fiber tracts projecting to upper limb muscles from single pulse TMS we will create anatomically accurate computational brain models using MR images from ten nonimpaired individuals. The brain models we develop will incorporate anatomical features, including fiber tracts, from magnetic resonance imaging (MRI) data we record from these ten nonimpaired participants. We will record neurophysiologic data from the same ten nonimpaired participants in order to test for correlations between biceps and FDI motor evoked potentials before and following iTBS with modeled induced electric fields acting on their corresponding cortical fiber tracts.

## Human Subjects

Ten nonimpaired individuals will be recruited for participation. All subjects will complete and sign a safety questionnaire to verify that they are free of contraindications for MRI and TMS. All subjects will provide informed written consent. We will seek study approval from the VCU Institutional Review Board.

## Magnetic Resonance Image Acquisition (Session 2 or 3)

[figure not shown]
T1-weighted images will be acquired using a 3D MPRAGE sequence (time echo (TE)/time repetition (TR)=3.2/6.8 ms acquired sagittally with a 1.0x1.0x1.2 mm resolution at a flip angle of 9°, echo train length (ETL) = 240, matrix=256x240). T2-weighted images will be acquired using a 3D multishot turbo spin echo sequence (TE/TR=245/2500 ms acquired sagittally with a matching resolution of the T1-W images, two averages, flip angle=90°, ETL=133, matrix=256x256). DTI images will be acquired using a high resolution single-shot spin echo EPI sequence (TE/TR=89/5700 ms acquired axially with a 1.7 mm isotropic resolution at a flip angle of 78°, ETL=141, matrix=140x140, max b-value=2000 s/mm^2, 96 directions).

## Computational Brain Modeling and Simulation of TMS

We will use MRI data from ten nonimpaired individuals to create 3D head and brain models of each individual. Using the software Freesurfer, along with high-resolution T1 and T2 weighted images, we will create high-resolution anatomically accurate models with differentiated skin, bones, cerebrospinal fluid, grey matter, white matter, and ventricles within the brain. The Freesurfer software we will use is open-source and developed for analyzing MRI images for development of 3D models. We will input MRI slices and use contrast information to estimate anatomical boundaries, such as that between the skin and skull, or between grey matter and white matter. A 3D mesh is then created using these estimated boundaries and other geometrical information taken directly from the input MRI data.

We will use high resolution DTI data and extract fiber tracts using a graphical toolbox ExploreDTI. Fiber tracts are constructed using whole brain tractography. Tracts will be drawn from a seed region of interest, such as M1, with seed fractional anisotropy threshold of 0.2, minimum fiber length of 50 mm and angle threshold of 30 degrees. Coordinates of tracts are imported into SolidWorks and

extruded to a solid, 3D line. These 3D fiber models are exported as .STL files for finite element analysis in Sim4Life. Figure 3 shows on the left the fiber tracts originating from M1, and on the right fibers being stimulated by a figure-of-eight TMS coil. The fiber models will be embedded into our 3D head models to calculate the induced electric field during TMS in different regions of the brain.

**Fig. 3.** M1 fibers will be extracted from DTI MRI. Isolated fiber tracts will be exported as 3D objects in order to simulate the induced electric field from TMS on the 3D fibers at regions of interest in the brain.

Using finite element analysis, we will determine the induced electric fields acting on isolated fiber tracts by simulating TMS in Sim4Life software. We will specify material properties (see Table 2), grid details, and the current source, similar to our previous work. Induced electric fields will be calculated using the Slice Viewer and Surface Viewer utilities within Sim4Life. Voxels stimulated above a threshold electric field of 150 V/m will be recorded.

**Table 2.** Material properties we will specify in Sim4Life simulations of TMS.

Structure	Mass Density ( $kg/m^3$ )	Electric Conductivity (S/m)
Skin	1109	0.17
Skull	1908	0.32
CSF/Ventricles	1007	1.7765
Grey Matter	1044.5	0.239149
White Matter	1041	0.26507
Cerebellum	1045	0.659667

[figure not shown]
### **Transcranial Magnetic Stimulation in Human Subjects**

Subjects who underwent MR imaging, will also participate in two sessions of TMS. Each TMS session will consist of baseline measures of MEPs in response to single pulse TMS, followed by the iTBS protocol. One iTBS session will target the biceps, and one session will target the FDI. Each session will consist of active iTBS applied to the hotspot of the target muscle, and sham iTBS. Sessions will be separated by at least 3 days to minimize the potential for carry over effects. Before and 10, 20 and 30 minutes after each iTBS session, MEPs will be recorded in order to quantify corticomotor excitability similar to our preliminary work.

Subjects will be instrumented with surface electromyography (EMG) electrodes on their dominant arm after the skin is shaved and cleaned with alcohol wipes. Surface EMG electrodes (disposable Ag-AgCl, Noraxon) will be located over the biceps and the FDI. EMG signals will be amplified (x1000) and bandpass-filtered prior to A/D conversion (CED Micro 1401 MkII, Cambridge Electronic Design). All EMG data will be sampled at 2 kHz using Spike2 software (Cambridge Electronic Design) and stored on a personal computer for offline analysis.

Prior to the iTBS session, the maximal compound muscle action potential (Mmax) will be recorded from the target muscle (biceps or FDI). The amplitude of Mmax is required to normalize MEP amplitudes.

To record Mmax, single pulse electrical stimuli, 0.2 ms pulse width will be delivered to Erb's point via a bipolar stimulating electrode (0.47 cm^2; 2.5 cm inter-electrode distance) connected to a constant current stimulator (DS7AH, Digitimer Ltd.). To determine RMTs and record MEPs, single pulse TMS will be delivered to the motor cortex contralateral to the resting target arm using a Super Rapid Plus stimulator via a 70 mm figure-of-eight coil. The vertex at the intersection of the inion-nasion and inter-aural lines will be marked on a linen cap tied snugly on the subject's head. The coil will be held tangentially on the scalp via a support stand with the coil center rotated to induce a posterior-to-anterior cortical current across the central sulcus. The hotspot for the target muscle will be identified as the location evoking the largest peak-to-peak amplitude MEP using the lowest stimulation intensity. Resting motor threshold (RMT) will be determined as the lowest stimulus intensity that induces MEPs of  $\geq 50 \mu\text{V}$  in at least 5 of 10 consecutive stimuli with the target muscle fully relaxed. The stimulus intensity for ensuing single pulse MEP trials will be set at 120% of RMT. To record MEPs, the stimulator will be triggered to deliver 15 stimuli at a rate of 0.2 Hz. Active motor threshold (AMT) will then be determined during sustained contractions of 20% the subject's maximum effort. With visual feedback provided relative to their maximum EMG root mean squared value, subjects will sustain a 20% maximum effort contraction of the target muscle during which AMT will be determined as the stimulus intensity that elicits a MEP  $\geq 200 \mu\text{V}$  in at least 5 of 10 consecutive stimuli.

**Fig. 4.** The biceps and FDI will be targeted for the iTBS protocol in nonimpaired subjects. All subjects will be seated with the arm supported against gravity in the horizontal plane. The intensity of all iTBS pulses will be 80% of the subject's active motor threshold (AMT). Before each iTBS session (iTBS 1 and 2, which are sham and active, respectively), RMTs and motor evoked potentials (MEPs) will be recorded. MEPs will also be recorded at 10 minute intervals following iTBS.

Intermittent TBS stimulation will be applied using a Magstim Super Rapid Plus stimulator and a 70 mm double air film coil that includes a built-in cooling system to maintain operating temperature. iTBS applied to the target muscle will consist of three pulses presented at 50 Hz, repeated every 200 ms for 2 s at an intensity of 80% AMT. Two second bursts will be repeated every 8 s for a total of 600 pulses (Figure 4). For the sham condition, a sham coil (Magstim 70mm double air film sham coil), looking identical to the active coil and making a similar noise but without delivering any active stimulation, will be applied to the hotspot of the target muscle. Throughout each session subjects will wear earplugs, be kept unaware of the type of stimulation, and be presented with nature videos to control engagement.

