#### **Data and Statistical Analysis**

We will calculate the root mean square (RMS) amplitude of the evoked response, the RMS amplitude of the pre-stimulus background EMG (over a duration of approximately 25 ms matched to the

duration of the corresponding evoked response), and the peak-to-peak amplitude of the evoked response (MEP or M-wave) using purpose-written Matlab code (The MathWorks, Inc.). Stimulus events where the pre-stimulus RMS amplitude is larger than the evoked response, or where voluntary activity is detected, will be discarded to ensure similar levels of background activity across subjects and trials. MEP amplitudes will be normalized by their corresponding Mmax amplitudes. All patient characteristics, including RMTs and AMTs, will be summarized using means and standard deviations. The overall mean and standard deviation of MEPs (normalized to Mmax and unnormalized) will be reported. Linear mixed effect models will be used to determine the overall mean difference between the normalized MEP amplitudes between the active and sham protocols. Separate mixed effect model analyses will be used for each muscle (biceps and FDI), condition (sham and active) and time point following iTBS (in total 12 mixed effect models). Since this is a pilot study, all inference will be performed at the 0.25 level and no adjustment for multiple comparisons will be made. Pearson correlation coefficients will be computed to test for correlations between mean MEPs in response to single pulse TMS (before iTBS protocol) and the maximum induced electric field. A strong correlation between MEPs and induced electric fields would indicate a strong relationship between our experimental and computational outcome measures and provide a foundation for our future work. Pearson correlation coefficients will also be computed to test for correlations between mean MEPs following iTBS and maximum induced electric fields to determine whether greater induced electric fields indicate a participant is more responsive to the iTBS protocol.

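### Recording MEPs at 120% of each person's own RMT removes differences in field gain, which weakens the MEP-field correlation as a check of the anatomy hypothesis; RMT and AMT, which carry that gain, are only summarised

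*Combined protocol and SAP*

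**What the plan says.** The Approach section holds that brain anatomy determines the field TMS induces and that this field drives the effect of treatment. It sets the aim of correlating biceps and FDI MEPs, before and after iTBS, with modelled fields in ten people.

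Under Transcranial Magnetic Stimulation in Human Subjects, "Resting motor threshold (RMT) will be determined as the lowest stimulus intensity that induces MEPs of" at least 50 µV in five or more of ten stimuli. Then "The stimulus intensity for ensuing single pulse MEP trials will be set at 120% of RMT". No other intensity is given for the MEPs recorded after iTBS, and the iTBS itself is set at 80% of the person's AMT.

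Under Data and Statistical Analysis, Pearson coefficients test for "correlations between mean MEPs in response to single pulse TMS (before iTBS protocol) and the maximum induced electric field", and also for "correlations between mean MEPs following iTBS and maximum induced electric fields". The plan reads the baseline result as validation: "A strong correlation between MEPs and induced electric fields would indicate a strong relationship between our experimental and computational outcome measures". RMT and AMT enter only descriptively: "All patient characteristics, including RMTs and AMTs, will be summarized using means and standard deviations".

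Under Computational Brain Modeling and Simulation of TMS, the authors will specify material properties, "grid details, and the current source, similar to our previous work". Whether the simulated current is the same for everyone or follows each person's threshold is not stated.

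**The concern.** On the plan's own premise, someone whose anatomy yields more field per unit of output reaches the 50 µV criterion at a lower output. The anatomical difference therefore appears in RMT. Testing everyone at the same multiple of their own RMT adjusts for that difference before the MEP is recorded, and the plan then looks for it in the MEP.

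What is at stake is how the study's main link between experiment and model is read. A null could be taken as evidence against the computational model, or against the anatomy hypothesis, when the measurement had removed much of the signal. A positive result is hard to interpret while the simulated current is unstated. All inference is at the 0.25 level without adjustment, so one null correlation in four would be called significant anyway. The quantities that should track the modelled field most directly are collected but not analysed against it.

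**Working it through.** **The plan's own figure.** The only sample-size calculation (Biostatistical Justification) concerns active against sham: difference 5%, SD 9%, correlation 0.5, two-sided alpha 0.25, power at least 80%, n = 10. Averaging three post-iTBS differences per person gives an SD of 9 × √[(1 + 2 × 0.5)/3] = 7.35, and the noncentral t gives 82.2% power at n = 10. The figure reproduces on that reading, but it says nothing about the MEP-field correlation, for which no power is given.

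**The cancellation.** Let g be field per unit of stimulator output (the anatomical gain) and E* the field at which the person meets the 50 µV criterion.

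- RMT = E*/g.
- Field delivered at 120% RMT = g × 1.2 × E*/g = 1.2E*. The gain drops out.
- *Common simulated current:* the modelled field is proportional to g, but the MEP was recorded at a delivered field of 1.2E*, which does not contain g.
- *Simulation at each person's 120% RMT:* the modelled field is 1.2E*, so it does not contain g either.
- RMT = E*/g does contain g, and should fall as the common-current field rises. The same argument applies to AMT with its own criterion.

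**Illustration.** The documents give no between-person variances, so these are assumptions: gain CV 10-20%, threshold CV 5-20%, RMT measurement error 3%, log-MEP noise SD 0.5, gain independent of threshold. There were 20,000 simulated trials of n = 10 for each combination. The critical value at two-sided alpha 0.25 with 8 df is |r| = 1.240/√(8 + 1.240²) = 0.402. In the base model, MEP = exp(3 ln(drive) + noise), where drive is the delivered field divided by E*.

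| Correlation | Mean r | Declared significant |
|---|---|---|
| MEP with common-current field, scalar gain only | 0.00 | about 25% |
| RMT with common-current field, no field-model error | -0.42 to -0.94 | 59-100% |
| RMT with common-current field, 15% field-model error | weaker | about 36-96% |

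At gain CV 15% and threshold CV 10%, the RMT figure is 98% without field-model error and about 78% with 15% error.

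If the simulation uses individual intensities, the result for MEP against field depends on the assumed recruitment curve: 24-27% in the base model, and 25-68% (mean r +0.05 to +0.49) with other recruitment forms. Any excess over 25% comes from threshold variation and RMT error, not from gain.

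**When anatomy also acts above threshold.** If log-MEP at 120% RMT also rises with log gain, with coefficient 1, 2 or 3 (gain CV 15%), MEP against common-current field is significant in about 38%, 65% and 84% of trials.

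**The case against.** The strongest reply is that the 25% is built in. Once anatomy is a single gain and everyone shares one recruitment slope, the drive at 120% RMT is 1.2 times measurement error, and simulation can only return alpha. The plan's idea of anatomy is wider: it refers to fibre tracts, and it records voxels above 150 V/m, which is a spatial extent. Equal multiples of threshold do not ensure equal recruitment above threshold. This stands, and the 38-84% figures show its possible size.

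A reader might therefore infer too much from the cancellation: that the planned correlation is insensitive whatever the simulated current, that a null is to be expected even if the hypothesis is true, or that any significant result is mostly chance. The documents support none of these. They give nothing on how anatomy affects recruitment above threshold, and the individual-intensity figure varies too much with assumptions to be called the false-positive rate.

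Two further points stand. The 59-100% for RMT assumes the modelled field is exact, although it comes from segmentation, tractography and one set of conductivities for everyone; the range with field-model error must be shown beside it. And the MEP-field correlation is the aim stated in the Approach section, so making it secondary would alter the study's aim.

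What does not fall is the cancellation itself, which follows from the plan's RMT definition and its stated premise, and the absence of any planned analysis of RMT or AMT against the field.

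**Conclusion.** The concern holds in limited form. Threshold-scaled intensity removes field gain per unit output from one side or the other of the MEP-field correlation, and so weakens it as a check of the anatomy hypothesis. It does not make a null certain. The post-iTBS correlation shares the weakness, because its test pulses are scaled to RMT and the iTBS to AMT.

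The algebra is exact for gain only, and takes modelled current as proportional to stimulator output. The percentages are illustrative and rest on assumed CVs, independence of gain and threshold, and, for the lower RMT range, an assumed 15% field-model error. Within the scalar-gain model the contrast is about 25% for MEP against 36-96% or 59-100% for RMT; outside it, the MEP correlation can do considerably better than 25%. The unstated simulated current is a gap in its own right, because it decides what a non-zero correlation would mean. The correction improves the analysis at almost no cost and does not require demoting the planned correlation.

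**What to change.** Three changes of wording:

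1. In Computational Brain Modeling and Simulation of TMS, state that the simulation is run at one common coil current for all participants. Report any run at individual intensity separately. A field computed at 1.2 × RMT contains RMT, so it should not be used as the predictor for RMT.
2. In Data and Statistical Analysis, add for each muscle the correlation of RMT with the maximum modelled field on that muscle's tract at the common current, with AMT as support. State the expected sign (negative). Keep the planned MEP-field correlations in their present place.
3. In the same section, state that threshold-scaled intensity removes gain differences from the MEP-field correlations, so a null there alone is not evidence against the anatomy hypothesis.

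The cost is two to four extra correlations on RMT, AMT and imaging data already to be collected, plus common-current simulations if those were not already intended. The extra tests add to the unadjusted testing at 0.25, so they should be reported with estimates and intervals. No stimulation intensity, visit or participant number changes.

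### The 12 mixed models are split by condition, so none contains the active–sham difference that the plan promises and powers, and the pre-iTBS MEP has no stated role in that comparison

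*Combined protocol and SAP*

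**What the plan says.** **Target and models.** Data and Statistical Analysis says that linear mixed models will "determine the overall mean difference between the normalized MEP amplitudes between the active and sham protocols". It then specifies: "Separate mixed effect model analyses will be used for each muscle (biceps and FDI), condition (sham and active) and time point following iTBS", and gives the total as 12. It names no change score, baseline covariate or period term. The only analysis in which it names the pre-iTBS MEP is the Pearson correlation with the maximum electric field.

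**Powered analysis.** Biostatistical Justification powers a two-sided test of the overall mean active–sham difference in a repeated measures model: ten participants, difference 5%, SD 9%, correlation 0.5 between differences within an individual, type I error 0.25, at least 80% power.

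**Design.** Under Transcranial Magnetic Stimulation in Human Subjects there is one visit per muscle: "Each session will consist of active iTBS applied to the hotspot of the target muscle, and sham iTBS". On recordings: "Before and 10, 20 and 30 minutes after each iTBS session, MEPs will be recorded in order to quantify corticomotor excitability". Below, a block means one iTBS application, sham or active, with its own recordings. The body text gives no order for the two blocks within a visit. The Fig. 4 legend does: "Before each iTBS session (iTBS 1 and 2, which are sham and active, respectively), RMTs and motor evoked potentials (MEPs) will be recorded". No section mentions a randomised or counterbalanced order. The gap of at least 3 days separates the two muscle visits, not sham from active.

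**Test intensity.** "The stimulus intensity for ensuing single pulse MEP trials will be set at 120% of RMT". The text does not say whether this is reset from the RMT re-measured before the second block, nor whether Mmax is recorded again for each block.

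**The concern.** A model fitted to one condition has no active–sham parameter. The models as listed therefore cannot deliver the comparison that the same paragraph promises, and whoever analyses the data will have to devise it afterwards. That choice includes how to use the pre-block MEP, on which the plan is silent.

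The choice matters more if sham always comes first. Condition and block then coincide, and a comparison of post-iTBS values alone cannot tell an iTBS effect from a shift in measured MEP between the first and second block. Such a shift could create an apparent effect or hide a real one. What is at stake is how the pilot's active–sham estimate is interpreted; the electric-field correlations do not use this contrast.

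**Working it through.** **1. Model count.** 2 muscles × 2 conditions × 3 post time points = 12. With both conditions in the same model the count would be 2 × 3 = 6, or 2 if the time points were also pooled. Only separation by condition reaches 12, so this is unlikely to be loose wording.

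**2. The plan's sample size.** Inputs from Biostatistical Justification: difference 5, SD 9, correlation 0.5, two-sided alpha 0.25. If the 0.5 applies across the three post time points (an assumption; the repeats are not named), the SD of a participant's mean difference is 9 × √[(1 + 2 × 0.5)/3] = 7.35. With n = 10 the noncentrality is 5/(7.35/√10) = 2.15 and the critical t on 9 df is 1.23, giving power 82.2%; n = 9 gives 79.0%. So n = 10 is reproduced, by an analysis that is none of the 12 models. If the 0.5 applies across the two muscles, the SD is 9 × √0.75 = 7.79 and power is 78.9% (81.0% by normal approximation). A single time point (SD 9) has 70.8%.

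**3. What drift does.** Let θ be the active–sham effect and δ the shift in measured MEP from the first to the second block. The post-only contrast has expectation θ + δ. The change-from-baseline contrast has expectation (θ + δ at post) − (δ at second baseline), which equals θ when the shift is already fully present at the second baseline. Rejection rate of the post-only contrast with θ = 0, n = 10 and noncentral t (δ is assumed throughout):

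| δ (points) | One time point, SD 9 | Mean of three, SD 7.35 | Two-muscle reading, SD 7.79 |
|---|---|---|---|
| 0 | 25% | 25% | 25% |
| 1 | 28% | 29% | 28.5% |
| 2 | 35% | 40% | 38% |
| 3 | 46% | 54.5% | 52% |

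If resetting the test intensity absorbed half of a 2- or 3-point drift (also assumed), the residual would be 1 or 1.5 points: 28% or 31% at one time point, 29% or 34% on the mean of three. In the other direction, drift of −2 or −3 points cuts correct-direction power for a 5-point effect from 82% to 54% or 37% (mean of three). The change score stays at 25% under the null for drift fully present at the second baseline.

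**4. Price of the change score without drift.** Its variance on the three-time-point mean is 7.35² + s² − 2 × covariance, where s is the SD of the baseline active–sham difference and r its correlation with the post difference. The documents give neither s nor r. Power for 5 points:

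| r | s = 7.35, r with the post mean | s = 9, r with the post mean | s = 9, r between single recordings |
|---|---|---|---|
| 0 | 63% | 57% | 57% |
| 0.3 | 73% | 66% | 69% |
| 0.5 | 82% | 75% | 82% |
| 0.7 | 94% | 88% | 98% |

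Break-even with the post-only 82% is at r = 0.50, 0.61 and 0.50 respectively.

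**5. Random effects.** The three change scores in a block share one baseline, so their errors are correlated within a block. In 40,000 simulated null trials (SD 9 per recording, 0.5 between post differences, r between single recordings), a model with a participant-by-block effect held type I error at 25% for every r. With a participant effect only it was 52%, 47% and 34% at r = 0.3, 0.5 and 0.7.

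**The case against.** *The order rests on one parenthesis.* It does, in a figure legend, and that legend also applies the word session to a single block where the body text uses it for a visit. So the drift argument is secondary and conditional. The model mismatch needs no assumption about order.

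*A pre–post contrast was probably intended.* This is a natural sense of a model per muscle, condition and post time point, and it would use the block baseline. But it is not stated, and finding a change under active and none under sham is not a test of the difference between them. The active–sham test would still be missing.

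*The drift is invented.* Its size and direction are assumed. At 1 point the inflation is small (28–29% against 25%); 2 and 3 points are 40% and 60% of the planned 5-point effect. The figures only illustrate sensitivity.

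*The plan already has safeguards.* Participants will "be presented with nature videos to control engagement", stimulus events with voluntary activity or high background EMG are discarded, and sham first avoids carry-over from active to sham. A reset intensity or a per-block Mmax could absorb some drift, if done. These may reduce drift but do not separate order from condition.

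*It is a pilot.* "Since this is a pilot study, all inference will be performed at the 0.25 level", with no multiplicity adjustment. That limits the consequence; it does not supply the missing contrast.

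A reader might infer that the trial's type I error is 40% or more, or that the plan has chosen a post-only comparison. The documents support neither: they give no drift, and they state no active–sham model at all, post-only or otherwise.

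**Conclusion.** The plan is wrong as written on one point that needs no assumption about order or drift: none of its 12 models can estimate or test the active–sham difference it sets out to determine, and none is the repeated measures analysis for which ten participants give about 82% power (on the three-time-point reading). It also leaves the pre-block MEP without a role in that comparison.

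The second part is conditional. If the legend's order is fixed, if the contrast is taken on post-iTBS values alone, and if measured MEP drifts between blocks, the drift passes into the estimate one for one. The illustrative rates of 29%, 40% and 54.5% depend on all three conditions and would be lower to the extent that resetting intensity or Mmax for each block absorbed drift. It would be too strong to say that the design is shown to be biased. The plan should be corrected before analysis. Confidence is medium, and the effect is on interpretation of a small pilot.

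**What to change.** - Replace the 12 models with one mixed model per muscle containing both conditions and all three post time points, with participant and participant-by-block random effects, and state the active–sham contrast explicitly.
- Bring each block's own pre-iTBS normalized MEP into that contrast. Change from block baseline removes drift already present at the second baseline. A baseline-covariate version, reported alongside, removes only part of it, by an amount that depends on variance components the documents do not give. Pre-specify which version is primary.
- State in the text whether the legend's order holds for every participant and visit, and whether test intensity and Mmax are re-established before the second block.
- If the order is fixed, say in the conclusions that drift arising after the second baseline cannot be separated from the active effect.

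The cost is rewording and a little analysis on recordings the plan already makes. The statistical price is the possible loss of power tabulated above: if the baseline–post correlation of the differences is expected to fall below about 0.5 to 0.6, the change score is less powerful than a post-only contrast when there is no drift. That trade-off should inform the choice of primary version.
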